**REGULATORY FRAMEWORK:**

Please indicate all that apply:

	DOD (Department of Defense)
	DOE (Department of Energy)
	DOJ (Department of Justice)
	ED (Department of Education)
	EPA (Environmental Protection Agency)
	FDA (Food and Drug Administration)
	HHS (Department of Health and Human Services)
	VA
	Other:

Is this a clinical trial under ICH-GCP E6?  Yes  No

If yes, please confirm that the research team is familiar with and agrees to comply with the investigator requirements cited in ICH-GCP E6.  Yes  No

ICH-GCP E6 can be accessed by copying and pasting this URL into your browser:

<http://www.fda.gov/downloads/Drugs/Guidances/ucm073122.pdf>

## 1. Objectives

The objective of this research is to perform a non-blinded, non-inferiority randomized controlled trial to assess the quality of life (QOL) of women with stress urinary incontinence (leakage of urine with cough or sneeze) before and after conservative treatment with either pelvic floor physical therapy (PFPT) or home biofeedback. The target population are patients with stress urinary incontinence (SUI) who are seeking care and desire non-surgical management. Our central hypothesis is that home biofeedback will be non-inferior to pelvic floor physical therapy and both will equally improve quality of life for women with stress urinary incontinence. The specific aims are:

**Aim 1:** To compare quality of life, as measured by the International Consultation Incontinence Questionnaire-Short Form (ICIQ- SF), in women with stress predominant incontinence before and after PFPT versus home biofeedback application after 3 months of therapy. Secondary outcomes related to this aim include improvements in urinary incontinence severity as measured by the Incontinence Severity Index (ISI) and desire to pursue additional therapy (such as pessary or surgery) at the conclusion of the study.

**Hypothesis:** Home biofeedback will demonstrate equal improvement in QOL in women with SUI compared to PFPT.

**Aim 2:** To perform a comparative analysis of cost between PFPT treatment and home biofeedback for stress predominant incontinence as well as patient preference for either PFPT vs home biofeedback. **Hypothesis:** Home biofeedback will be less expensive than PFPT due to decreased copays, driving to visits, with similar success rates and women will prefer to have home therapy.

**Aim 3:** To determine whether patients experience improvement in sexual function following treatment using the Pelvic Organ Prolapse Incontinence Sexual Questionnaire- 12 and Female Sexual Function Index (FSFI). **Hypothesis:** Both groups will report improved sexual function.

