**PROTOCOL TITLE: SQEASI: Systematized Quality Exercise Alternatives for Stress Incontinence**

the community outpatient rehabilitation referral is often limited for patients in rural areas that must travel to larger city centers for PFPT. Women who live far from PFPT facilities also must travel great distances to see medical providers for their incontinence and attend multiple PFPT appointments. Though physical therapists have used biofeedback for 20 years, several FDA approved devices for home biofeedback have been introduced to help treat women with SUI at home. Regarding these devices, there is limited information available comparing them to the standard of care. If home biofeedback is equivalent to standard of care PFPT for SUI, patients can obtain treatment in the privacy of their homes with a home devices that may offer similar quality of life improvements for SUI without the inconvenience of travel, cost and personal distress as PFPT. To solve the problem of limited PFPT services and the obstacles obtaining PFPT, we propose to study at home biofeedback devices versus PFPT for women with SUI. This innovative research shows promise in helping our patients overcome an embarrassing and costly condition in the privacy of their own homes on their own time.

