### **3. Study Design**

We plan to perform an unmasked, non-inferiority randomized controlled trial to determine if quality of life is improved with use of PFPT or home biofeedback linked to smartphone for stress urinary incontinence. The target population are those patients with stress urinary incontinence who present to the urogynecology clinic either at University of New Mexico Hospital (UNMH) or Sandoval Regional Medical Center (SRMC). Women will be informed which arm of the study they are randomized to as this is required for treatment. Masking is not possible with this study design, as participants either do or do not receive a biofeedback device. All women will give written consent prior to enrollment.

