## 5. Number of Subjects

The primary outcome of this study is improvement in incontinence quality of life as measured by the ICIQ-SF Questionnaire. We used the previously reported means and standard deviation for this questionnaire (3) from a prior RCT on biofeedback and pelvic floor exercises. We have powered the study based on a 4-point difference as significant between groups. This 4-point difference used for the power calculation is based on prior studies and the minimally important difference that has been previously established (4). To achieve power for this non-inferiority RCT demonstrating a difference between groups of less than 4 points we need 21 patients per group (biofeedback versus PFPT) to detect no difference with an alpha =0.05 and

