### 7. Study Endpoints

The **primary endpoint** of our study is to determine the 3 month change in ICIQ-SF score between the women who undergo PFPT compared to those who undergo home biofeedback therapy for stress urinary incontinence. Our secondary endpoints include patient report of symptomatic cure or improvement and cost effectiveness between techniques and cost of intervention. Our **exploratory endpoints** are to investigate compliance with treatment between groups, preference if given choice between options, and differences in sexual function 3 months after initiation of therapy between the two groups. Desire for further treatment will also be assessed.

Given the extremely low-risk nature of the therapeutic interventions, we do not have any **safety endpoints**.

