## **13. Data Analysis**

Data Analysis: Between and within group differences will be evaluated using Fisher's exact test for categorical variables and t-tests for continuous variables. If there are any baseline differences between groups, a multivariate analysis will determine the contribution of these differences to observed differences (if any) between groups.

Power Analysis: Power analysis was performed based on previously reported means and standard deviation for the ICIQ-SF questionnaire. The primary outcome of this study is improvement in incontinence quality of life as measured by the ICIQ-SF Questionnaire. We used the previously reported means and standard deviation for this questionnaire (10) from a prior RCT on biofeedback and pelvic floor exercises. We have assumed a change score of greater than 4 points to be significant between groups based on prior studies and the minimally important difference that has been previously established (11). To achieve significance for a non-inferiority study using these assumptions we would need 42 patients, 21 per group to detect this difference with alpha =0.05 and with 80% power. To allow for a dropout of 20% we will enroll at least 50 patients, but up to 75 to account for participants who are lost to follow up.

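### The trial is labelled non-inferiority, but its ICIQ-SF hypothesis and power statement are worded as equality within 4 points, and 21 per group can give exactly 80% power for at most one of the two

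*Combined protocol and SAP*

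**What the plan says.** The design label is consistent. Sections 1, 3, 5, 12 and 13 all say non-inferiority; Section 3, for example, has "We plan to perform an unmasked, non-inferiority randomized controlled trial".

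The hypotheses and the power statements do not keep to that label:

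- **Section 1, central hypothesis:** "home biofeedback will be non-inferior to pelvic floor physical therapy and both will equally improve quality of life". Both ideas stand in one sentence.
- **Section 1, Aim 1 (the ICIQ-SF aim), its only hypothesis:** "Home biofeedback will demonstrate equal improvement in QOL in women with SUI compared to PFPT".
- **Section 2, rationale:** "If home biofeedback is equivalent to standard of care PFPT for SUI".
- **Section 5, sample size:** "We have powered the study based on a 4-point difference as significant between groups", then "To achieve power for this non-inferiority RCT demonstrating a difference between groups of less than 4 points we need 21 patients per group". That sentence goes on to name the absence of a difference as the thing to be detected, at alpha 0.05 and 80% power.
- **Section 13, power analysis:** a change score above 4 points is taken as significant between the arms, followed by "To achieve significance for a non-inferiority study using these assumptions we would need 42 patients, 21 per group to detect this difference".

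Section 7 defines the primary endpoint as "to determine the 3 month change in ICIQ-SF score between the women who undergo PFPT" and those on home biofeedback, without a direction. Section 13 plans t-tests for continuous variables. It gives no one-sided test, no confidence limit to be compared with 4, and no equivalence procedure.

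**The concern.** Non-inferiority asks one question: is home biofeedback worse than PFPT by 4 points or more? Equality or equivalence within 4 points asks a second one as well: is it better by 4 points or more? A difference of less than 4 points with no direction, taken literally, is the equivalence claim. The Section 13 wording, in which more than 4 points is significant, reads like a superiority difference. The same 21 per group, alpha 0.05 and 80% power are attached to all of these.

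Two things are at stake. First, with no decision rule, the criterion for success could be settled after the data are seen. Second, a non-inferiority result could be reported as showing equal improvement, which it does not establish and for which the trial may have less than 80% power.

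**Working it through.** **Inputs from Sections 5 and 13.** 4 points; 21 per group; alpha 0.05, sides not stated; 80% power; 20% dropout; 50 to 75 enrolled. The SD is cited from a published RCT, but no value is given.

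**Step 1. The plan's own figure.** Without an SD, 21 per group cannot be reproduced. It can only be solved backwards for the SD. With a true difference of 0 and the normal approximation, SD = 4 / [√(2/21) × (z_alpha + z_power)], where √(2/21) = 0.3086 and z_power is 0.842 for non-inferiority or 1.282 for equivalence at 80%.

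| Target of the 80% | Calculation | Implied SD |
|---|---|---|
| Non-inferiority, one-sided 0.05 | 4 / (0.3086 × 2.487) | 5.21 |
| Non-inferiority, one-sided 0.025 | 4 / (0.3086 × 2.802) | 4.63 |
| Equivalence, 0.05 per side | 4 / (0.3086 × 2.927) | 4.43 |
| Equivalence, 0.025 per side | 4 / (0.3086 × 3.242) | 4.00 |

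A two-sided 0.05 superiority calculation for 4 points gives 4.63, the same as the second row. The t-based values are slightly lower: 5.12 and 4.51 for non-inferiority, about 4.4 and 3.9 for equivalence. So 21 per group is compatible with every reading and identifies none.

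**Step 2. Power of one claim given the other.** At a true difference of 0 and the same alpha per side:

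- non-inferiority power = Φ(4/SE − z_alpha)
- equivalence power = 2Φ(4/SE − z_alpha) − 1 = 2 × (non-inferiority power) − 1

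If non-inferiority has 80%, equivalence has 2 × 0.80 − 1 = 60%. If equivalence has 80%, non-inferiority has (1 + 0.80)/2 = 90%. A t-based simulation of 400,000 trials agrees on both.

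**Step 3. Numbers analysed.** After 20% dropout, 50 enrolled leaves 40 (20 per group) and 75 leaves 60 (30 per group). Taking the SDs at which 21 per group gives non-inferiority 80%:

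| Per group | SD 5.21, 0.05 per side | SD 4.63, 0.025 per side |
|---|---|---|
| 20 | SE 1.648; 2Φ(0.782) − 1 = 57% | SE 1.463; 2Φ(0.774) − 1 = 56% |
| 21 | 60% | 60% |
| 30 | SE 1.346; 2Φ(1.327) − 1 = 82% | SE 1.195; 2Φ(1.389) − 1 = 84% |

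If non-inferiority used 0.025 and equivalence 0.05 per side, then at 21 per group SE = 4.63 × 0.3086 = 1.43 and equivalence power is 2Φ(1.157) − 1 = 75%; the t-based figure is 76%.

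**Step 4. When the verdicts split.** Let d be the observed difference (positive favours the device) and h = z_alpha × SE. Non-inferiority needs d − h > −4. Equivalence also needs d + h < 4. At 21 per group:

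- One-sided 0.05: h = 1.645 × 1.609 = 2.65, so the verdicts split above 4 − 2.65 = 1.35.
- One-sided 0.025: h = 1.960 × 1.428 = 2.80, so they split above 4 − 2.80 = 1.20.

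With the 90% interval, d = +1 gives −1.65 to 3.65 and passes both. d = +2 gives −0.65 to 4.65 and passes non-inferiority only.

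**Step 5. Illustration with an assumed true device benefit** (t-based SDs, 21 per group, simulated). At 1 point, non-inferiority is shown in 93-94% of trials and equivalence in 50-52%. At 2 points, the figures are 98-99% and 28-33%.

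**The case against.** The strongest reply is that this is loose wording and not a second test. Every design label is non-inferiority, both power statements use that word, and no section mentions an equivalence test or a two-sided margin. Equal improvement can also be read as the expected result, which is the true difference of 0 assumed in the power calculation. The Section 2 sentence is rationale, and the Aim 1 line carries no margin of its own. "One-sided" and "two-sided" are this review's terms, since the plan states neither. All of this stands as an account of what the authors probably meant. It does not clear Section 5, where the undirected difference is the stated target of the power calculation, and no decision rule elsewhere overrides it.

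Three stronger readings are tempting, and the documents do not support them:

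- **That the trial is underpowered.** The SD is missing. The 60% follows algebraically from placing the 80% on non-inferiority and is not independent evidence of a shortfall. If 21 was sized for equivalence, there is none.
- **That any result favouring the device passes one statement and fails the other.** Small benefits pass both (Step 4).
- **That opposite verdicts are the likely outcome.** That needs a true device advantage, such as the 2 points in Step 5, which nothing in the plan suggests.

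Enrolment up to 75 also softens the power gap at a true difference of 0. It does not remove the conflict: 50 is the stated minimum, and a larger sample does not say which claim is being tested.

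**Conclusion.** The inconsistency is real and should be corrected. One primary comparison is described as non-inferiority, as equality or a difference under 4 points, and as a significant change above 4 points. No margin direction, sidedness or confidence-bound rule decides between them. For a given SD and alpha per side, 80% power at 21 per group is exact for at most one of non-inferiority and equivalence.

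The size is conditional on an SD that the plan does not state. If the 80% is for non-inferiority (SD about 5.1 at one-sided 0.05 or 4.5 at 0.025), equivalence power at zero difference is about 60% with 21 per group, ranging from 56-57% with 20 to 82-84% with 30, and about 76% at 21 per group with mixed alphas. If the 80% is for equivalence, non-inferiority has about 90%. The practical risk is an unsupported claim of equality and a success criterion open to choice. It is not a demonstrated lack of power for non-inferiority.

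**What to change.** State one primary hypothesis in Sections 1, 5 and 13: the 3-month improvement in ICIQ-SF with home biofeedback is not worse than with PFPT by 4 points or more. Then:

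- **Section 1:** replace the Aim 1 hypothesis with this statement and remove the equality clause from the central hypothesis.
- **Section 2:** bring the equivalence wording into line.
- **Section 5:** remove the undirected difference, the phrase about detecting no difference, and the description of 4 points as significant. Name 4 points as the margin and give its direction.
- **Section 13:** remove the wording that treats a change above 4 points as significant. State the one-sided alpha and the SD used, and say that the 80% power applies to non-inferiority, after checking that the SD supports it at 21 per group.
- **Decision rule (Section 13):** declare non-inferiority when the confidence bound on the unfavourable side excludes a 4-point deficit for biofeedback, and make no claim of equality or equivalence from that result.

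The cost is text changes in four sections, with no added patients or data. The sponsor gives up an equality claim. Keeping one at 80% power would need about 29 to 30 per group analysed at the non-inferiority SDs: 2 × (5.21 × 2.927/4)² = 29.1, rounded up to 30, or 2 × (4.63 × 3.242/4)² = 28.1, rounded up to 29 (unrounded SDs used).

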## PROTOCOL TITLE: *SQEASI: Systematized Quality Exercise Alternatives for Stress Incontinence*

with 80% power. Allowing for a dropout of 20% we will enroll at least 50 patients (or 25/group), but up to 75 total.

This is a not a multi-center study. Data will be housed at the Eubank clinic

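### Aim 2 hypothesises similar success rates, but success is not defined and the planned test could show a difference, not similarity

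*Combined protocol and SAP*

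**What the plan says.** The Aim 2 hypothesis in Section 1 has a cost part and a benefit part: "Home biofeedback will be less expensive than PFPT due to decreased copays, driving to visits, with similar success rates". The sentence stating the aim itself names only cost and patient preference. Success appears only in the hypothesis and is not defined there or elsewhere.

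The nearest endpoint is in Section 7: "Our secondary endpoints include patient report of symptomatic cure or improvement and cost effectiveness between techniques and cost of intervention". No response categories, cut-off or expected rate are given for it. Section 12 collects a one-item global impression of improvement (PGI-I) at 3 months but does not link it to Aim 2.

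For analysis, Section 13 says: "Between and within group differences will be evaluated using Fisher's exact test for categorical variables and t-tests for continuous variables". It adds a multivariate analysis if the arms differ at baseline. The same section has a separate cost analysis, expressed as incremental cost per QALY with EQ-5D utilities.

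The only margin is on the ICIQ-SF. Section 5 sizes the trial for "demonstrating a difference between groups of less than 4 points we need 21 patients per group", and Section 13 repeats the figure: "we would need 42 patients, 21 per group to detect this difference with alpha =0.05 and with 80% power". On enrolment, Section 5 says: "Allowing for a dropout of 20% we will enroll at least 50 patients (or 25/group), but up to 75 total".

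**The concern.** Similar success is a claim that the arms do not differ by much. Supporting it takes a statement of how much is too much and an interval that excludes that amount. Fisher's exact test supplies neither, because its null hypothesis is equality. Failing to reject equality in a small trial says little about how far apart the rates may be.

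Aim 2's message would be that biofeedback costs less for about the same success. Section 2 explains the appeal: a home device that matches PFPT would spare women travel and expense. If the success part rests on a comparison that could easily overlook a sizeable loss, the saving could be presented as free of any loss of benefit when the data cannot show that. Correcting the analysis of the ICIQ-SF primary endpoint would not by itself supply a definition, margin or interval for success rates.

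**Working it through.** **The plan's own figure.** 21 per group is sized on the ICIQ-SF. The SD is not printed; Section 5 says only "We used the previously reported means and standard deviation for this questionnaire (3) from a prior RCT on biofeedback and pelvic floor exercises". The figure therefore cannot be confirmed or refuted. Solving n = 2(z_α + z_β)²SD²/margin² for SD, with n = 21, margin 4 and 80% power:
- one-sided 0.025: SD = √(21 × 16 / (2 × 2.802²)) ≈ 4.63
- one-sided 0.05: SD = √(21 × 16 / (2 × 2.486²)) ≈ 5.21

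Neither result bears on a success rate, so the trial has no stated size for this claim.

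**Inputs for the check**
- Evaluable patients per group: 21 (Sections 5 and 13); 30, from 75 × 0.8 / 2; 37, from 75 / 2 rounded down, with no loss. The minimum enrolment of 50 less 20% leaves 40, or 20 per group, so 21 is slightly generous.
- Test: two-sided Fisher's exact test at 0.05. The plan gives alpha 0.05 without stating sidedness, so two-sided is an assumption.
- Success rates: assumed, because the documents give none. PFPT is set at 80%, 70% and 60%, with biofeedback 20 or 30 points lower.

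**Method.** For each n, enumerate every pair of success counts (i, j), compute the Fisher p-value, and sum Bin(i; n, p₁) × Bin(j; n, p₂) over the pairs with p ≥ 0.05. The sum is the probability that the true loss is missed.

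| True rates (PFPT v biofeedback) | 21 per group | 30 per group | 37 per group |
|---|---|---|---|
| 80% v 60% | 0.809 | 0.702 | 0.618 |
| 70% v 50% | 0.842 | 0.741 | 0.676 |
| 60% v 40% | 0.849 | 0.743 | 0.688 |
| 80% v 50% | 0.597 | 0.404 | 0.286 |
| 70% v 40% | 0.640 | 0.439 | 0.340 |
| 60% v 30% | 0.640 | 0.439 | 0.340 |

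Widening the assumed PFPT rate to 50% to 90% at 21 per group gives 74% to 85% for a 20-point loss and 48% to 64% for a 30-point loss.

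**Single results at 21 per group**
- 15/21 v 8/21, an observed loss of 7/21 = 33 points: Fisher p = 0.062. The Newcombe 95% interval for the loss is 3 to 56 points.
- 15/21 v 15/21, identical observed rates: the Newcombe 95% interval is −26 to +26 points.

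**Could the trial carry its own margin on success?** With equal true rates p, one-sided 0.025 and 80% power, n per group = 2p(1 − p)(1.960 + 0.842)²/margin². For an illustrative 20-point margin and p = 0.7: 2 × 0.7 × 0.3 × 7.849 / 0.04 = 82.4, so 83. For p = 0.6 and 0.8 the results are 95 and 63. At 21 per group, power against that margin is about 26%, 29% and 37% for p = 0.6, 0.7 and 0.8. The planned enrolment cannot support such a claim.

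**The case against.** The strongest objection is that the documents do not commit to what a reader might infer.

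- **No stated rule.** A reader might conclude that the plan will call the rates similar whenever p exceeds 0.05. It does not say so. The Section 5 sample-size text does speak of detecting no difference, but about the ICIQ-SF. What stands is that the plan offers no route to a finding of similar success, not that it has adopted a wrong one.
- **Success may not be binary.** Section 7's cure or improvement is not tied to Aim 2, and success could point back to the ICIQ-SF result in Aim 1. This stands, so the Fisher figures are conditional on the Section 7 reading. It also makes a definition more necessary.
- **Aim 2 has its own analysis.** It would be wrong to say that Fisher's test is all that lies behind Aim 2. The cost-per-QALY analysis covers the cost part and sets cost against effect. It does not test whether success rates are similar.
- **The size can be overstated.** A reader might infer that a 20- to 30-point loss would simply pass. A 20-point loss usually would. A true 30-point loss at 21 per group is still detected 36% to 40% of the time under the rates tabulated, and at 30 or more per group it is detected more often than missed.
- **Secondary aim.** The primary result and the sample size are untouched. This limits the weight of the point but does not remove it.

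**Conclusion.** The concern holds in a limited form. Aim 2 contains a similarity claim on an undefined outcome. If that outcome is patient-reported cure or improvement, the planned comparison cannot support the claim, and no margin applies to it. At the planned 21 per group, a true 20-point loss would go undetected about four times in five or more, and a 30-point loss about three times in five. Enrolling all 75 eases this but does not cure it: even with no dropout, a 20-point loss is missed 62% to 69% of the time.

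These sizes rest on assumed PFPT success of 60% to 80%, a two-sided 0.05 test and a binary outcome. That the test cannot establish similarity does not depend on the assumed rates. The consequence is confined to Aim 2's joint conclusion on cost and success. It should be corrected, but it does not threaten the primary endpoint.

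**What to change.** In Section 13:
1. State which item counts as success, for example patient-reported cure or improvement at 3 months, and which responses qualify.
2. Report the risk difference (biofeedback minus PFPT) with its 95% confidence interval, for instance Newcombe's, alongside Fisher's test. Fisher's test need not be dropped. As 15/21 v 8/21 shows, the interval and the p-value can disagree near the boundary, so the interval should carry the interpretation.
3. State that a non-significant difference will not be reported as similar success.

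In Aim 2, replace the similarity clause. Make any conclusion of lower cost without loss of benefit conditional on the ICIQ-SF confidence interval excluding a disadvantage of 4 points for biofeedback. This works only if Section 13 also says that the ICIQ-SF will be judged by that interval; at present it names only t-tests for continuous outcomes. If the interval does not exclude the margin, report cost and effect differences side by side, with no similarity claim.

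The cost is protocol wording in Section 1 and Section 13, with no extra patients, visits or data. The trial gives up a stand-alone claim of similar success rates, which its sample cannot support.
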